4. STUDY DESIGN

This pilot study is a single-center, non-blinded, controlled clinical trial with evaluations at baseline; follow up assessments at months 3, 6, 12 and 18; and a final assessment at the end of study visit occurring at 24.

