7.5.4 Failure to Fit

Teeth randomized for treatment will be included in the study even if they cannot accommodate the crown and therefore a composite crown is placed instead (intention-to-treat principle). The investigator will keep record of the teeth for further adjustment in the analysis. The reason for the fitting failure will also be recorded (See Appendix 2). If the tooth needs to be extracted (not matching inclusion/exclusion criteria), it will be excluded from the trial.

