10. STUDY ASSESSMENTS

Clinical Assessments will be done at baseline post crown placement; at months 3, 6, 12 and 18; and end of study visit occurring in range of 24 to 30 months from baseline.

Assessments and documentation required at each assessment interval:

• Photographs of selected teeth	Baseline
• Photographs of tooth preparations	Baseline and when possible
• Photographs of cemented crowns	Baseline
• Photographs of occlusal and frontal views	Baseline and when possible
• Assessment of fit	All intervals
• Assessment of positioning	All intervals
• Assessment of proximal contact	All intervals
• Assessment of marginal adaptation	All intervals
• Assessment of color: match , staining/color change	All intervals
• Assessment of time placement	Baseline
• Assessment of gingival status	All intervals
• Assessment of retention	3, 6, 12, 18 and 24 mo
• Assessment of veneer/composite integrity	3, 6, 12, 18 and 24 mo
• Assessment of secondary caries	3, 6, 12, 18 and 24 mo
• Assessment of trauma	3, 6, 12, 18 and 24 mo
• Assessment of clinical pulp pathology	3, 6, 12, 18 and 24 mo
• Assessment of radiographic pulp pathology	24 mo
• Assessment of tooth	All intervals
• Assessment of parents' esthetic satisfaction	All intervals (baseline at 3-month follow up)

Non-recall assessment to be done at the time of tooth/crown lost to study due to trauma. If this was to occur, the patient would be discontinued from study and the justification recorded.

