11.0 DATA ANALYSIS

Descriptive statistics (means, standard deviations, counts, and percentages) will be calculated for all variables. To evaluate if the primary efficacy variables differ by the three treatment groups (NuSmile PVSCC Signature Crowns, NuSmile ZR, and Strip composite crowns), ANOVA or Chi-square tests of association will be performed.

All subjects evaluated at the 6-month interval or beyond and subjects who have lost crowns or teeth will be considered for efficacy. All enrolled subjects defined here as those who have had at least one crown placed will be evaluated for safety. Any missing, unused or false data will be omitted from data analysis.

The primary efficacy variables in this trial are fit, positioning, proximal contact, marginal adaptation, color match, gingival status, crown retention, veneer/composite integrity, secondary caries, occlusal integrity, history of trauma, clinical pulp pathology, parents' esthetic satisfaction. Scores for efficacy variables will be summarized and displayed using descriptive statistics (means, standard deviations, counts, and percentages).

Inferential statistics will be used to detect significant differences in the primary efficacy variables by the treatment status at baseline and at 6, 12, 18, and 24 month follow-up. Statistical differences will be calculated using logistic regression models accounting for within cluster variance using generalized estimating equations (GEE).

Safety variables include Adverse Events and Unanticipated Adverse Device Effects. All subjects that have had crowns placed will be evaluated for safety. Descriptions of occurrences, incidence, severity and required treatments for Adverse Events and Unanticipated Adverse Device Effects Will be summarized and tabulated where appropriate.

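### Radiographic pulp pathology is read once, at 24 to 30 months, and missing data are dropped, so a tooth extracted earlier for pulp disease leaves the rate instead of counting as a failure

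*Combined protocol and SAP*

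**What the plan says.** Section 10 (Study Assessments) lists "Assessment of radiographic pulp pathology 24 mo" and places the end-of-study visit between 24 and 30 months from baseline. The clinical reading is far more frequent: "Assessment of clinical pulp pathology 3, 6, 12, 18 and 24 mo".

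Section 11.0 (Data Analysis) states "Any missing, unused or false data will be omitted from data analysis". It keeps subjects with lost crowns or teeth in the efficacy set, but gives the lost tooth no outcome value. Its list of primary efficacy variables includes clinical pulp pathology and omits radiographic pulp pathology. The latter therefore receives only the descriptive statistics promised for all variables.

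Three other places bear on early tooth loss:

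- Section 7.5.4 (Failure to Fit) says "If the tooth needs to be extracted (not matching inclusion/exclusion criteria), it will be excluded from the trial". In context this concerns teeth found unrestorable at fitting, not later extractions.
- Section 10 provides an off-schedule assessment for one cause only: "Non-recall assessment to be done at the time of tooth/crown lost to study due to trauma". It continues: "If this was to occur, the patient would be discontinued from study and the justification recorded".
- Appendix 13 scores radiographic pulp pathology as absent or present, with no code for a tooth that was extracted, exfoliated or not filmed.

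**The concern.** Extraction is one consequence of pulp disease, so the chance that a tooth is still there to be filmed may depend on the outcome that the film is meant to measure. A tooth extracted for pulp disease at month 14, say, has no film at 24 months. Its missing value is omitted, so the tooth leaves both numerator and denominator.

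Loss before the film is foreseeable: Section 6.2 excludes only teeth expected to be lost within one year, while the film comes at two years or later.

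At stake is a by-arm percentage that readers may take as the pulp failure rate. Pulp outcome is a natural comparison here, because Section 7.5.2 removes different amounts of tooth in the three arms (about 25-30%, 20-25% and 15-20%).

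**Working it through.** The plan gives no rate of pulp failure, extraction or dropout, so there is no figure of its own to reproduce. The only count, 3 × 30 = 90 subjects, agrees with Section 5.

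**Inputs from the documents.** 120 to 200 crowns (Section 6) over three arms is 120/3 = 40 to 200/3 = 67 teeth per arm.

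**Assumed inputs.** p = true pulp pathology (10% or 20%); f = share of diseased teeth lost before the film (25% or 50%); g = share of healthy teeth lost or unfilmed (0 unless stated).

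**Formulas.** Film-only rate = p(1−f) / [p(1−f) + (1−p)(1−g)]. Film-only odds = true odds × (1−f)/(1−g).

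**Step 1, one arm, g = 0.**

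| True p | f = 25% | f = 50% |
|---|---|---|
| 20% | 0.15/0.95 = 15.8% | 0.10/0.90 = 11.1% |
| 10% | 0.075/0.975 = 7.7% | 0.05/0.95 = 5.3% |

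Teeth moved from failure to missing: from 40 × 0.10 × 0.25 = 1.0 to 67 × 0.20 × 0.50 = 6.7 per arm.

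**Step 2, direction when healthy teeth are also unfilmed (true 10%).**

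- f = 50%, g = 30%: 0.05/(0.05 + 0.63) = 7.4%, too low.
- f = g = 50%: 0.05/(0.05 + 0.45) = 10.0%, correct.
- f = 25%, g = 50%: 0.075/(0.075 + 0.45) = 14.3%, too high.

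**Step 3, two arms with true rates 20% and 10%, g = 0.** The true difference is 10.0 points and the true odds ratio is 0.25/0.111 = 2.25.

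| f, worse arm | f, better arm | Film-only rates | Difference (points) | Odds ratio |
|---|---|---|---|---|
| 25% | 25% | 15.8% v 7.7% | 8.1 | 2.25 |
| 50% | 50% | 11.1% v 5.3% | 5.8 | 2.25 |
| 50% | 25% | 11.1% v 7.7% | 3.4 | 1.50 |
| 25% | 50% | 15.8% v 5.3% | 10.5 | 3.38 |

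Equal shares leave the odds ratio alone but shrink the risk difference by 1.9 to 4.2 points, and percentages are what the plan will report. The arms would look identical only if (1−f worse)/(1−f better) = 1/2.25, for example 56% v 0% or 67% v 25%. Conversely, two arms that both truly have 10% would read 7.7% v 2.7% if f were 25% v 75%.

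**Step 4, scale.** The standard error of a 20% v 10% difference is √(0.20×0.80/n + 0.10×0.90/n): 7.9 points at n = 40 and 6.1 at n = 67, before clustering within child.

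**Step 5, traumatic loss (a separate matter).** If 5-15% of the 90 children have one (assumed), that is 4.5 to 13.5 children. At the average of 120/90 = 1.33 to 200/90 = 2.22 crowns per child, with one lost, 4.5 × 0.33 = 1.5 to 13.5 × 1.22 = 16.5 other crowns also go unfilmed. Section 6 allows four crowns per child, so the ceiling is 13.5 × 3 = 40.5.

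**The case against.** The strongest reply is that little depends on this rate. It is not a primary variable, no test is planned for it, and pulp failure is not an endpoint that the documents define. Clinical pulp pathology is primary and read at five visits, so symptomatic disease can be recorded before an extraction. Section 11 also tabulates "required treatments for Adverse Events and Unanticipated Adverse Device Effects", and counts for all variables would reveal how many teeth were filmed. All of this stands, and it limits the weight of the point. It does not repair the rate: none of these entries feeds it, and disease visible only on film is not covered by them. The assessment of the tooth at all intervals in Section 10 has no scale, so it cannot be assumed to score a lost tooth.

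A reader might infer more than the documents support:

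- *That the rate is always understated.* It is not. Section 6.2 leaves room for healthy teeth to be lost before the film too, and Step 2 shows the bias vanishing or reversing.
- *That the comparison favours a particular crown.* Nothing in the documents says that extraction of diseased teeth differs by arm. Section 4 says "This pilot study is a single-center, non-blinded, controlled clinical trial", so a difference cannot be ruled out, but neither its existence nor its direction can be derived.
- *That the trauma rule adds to the pulp bias.* As written it is not tied to pulp disease. It affects every outcome and mainly costs precision.

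**Conclusion.** The concern holds as a minor one. Followed as written, the plan drops pulp-related extractions from the radiographic rate in each arm. Understatement requires that diseased teeth go unfilmed more often than healthy ones. With no healthy loss and 25-50% of diseased teeth extracted first, it is about 4 to 9 points at a true 20% and 2 to 5 points at a true 10%, or roughly 1 to 7 teeth per arm. These rates are assumptions; the documents fix only the number of teeth. With equal shares across arms, the shift in the risk difference is smaller than its standard error in a pilot of this size. The case for acting is therefore a rate that means what readers will take it to mean, at very little cost.

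**What to change.** **Section 11.** Add a descriptive per-tooth outcome, pulp failure by 24 months: radiographic pathology at the final visit, clinical pulp pathology at any visit, or extraction or loss with pulp pathology before then. Report it beside the film-only rate, with teeth filmed, teeth not filmed and the reasons, by arm. Count teeth lost without pulp disease, or with unknown pulp status, separately and not as failures.

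**Section 10.** Extend the off-schedule assessment to every early tooth loss, recording the reason and the pulp status (the last clinical reading if the tooth is already gone). As a separate improvement that helps all outcomes, keep following a child's remaining crowns after one traumatic loss instead of discontinuing the child.

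**Cost.** Protocol wording, one form entry per lost tooth, and up to five already scheduled visits for each child retained (about 5 to 14 children under the assumed 5-15%). No research film is added and eligibility is unchanged.

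**Limits.** The reason for extraction is judged unblinded, which is why the film-only rate should stay alongside. Disease visible only on film in teeth lost early remains uncovered.

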APPENDIX 8: RETENTION

RETENTION	
A=	Intact
B=	Partially missing
C1=	Missing – no cement remaining on tooth or crown
C2=	Missing – some or all cement remaining on tooth
C3=	Missing – some or all cement remaining on crown interior (if crown available)
C4=	Missing – some cement remaining on both tooth and crown interior (if crown available)

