APPENDIX 12: CLINICAL PULP PATHOLOGY

CLINICAL PULP PATHOLOGY	
A=	Absent
B=	Present

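### The only unscheduled assessment is for trauma losses, so pulp failures extracted between visits and crowns recemented before a visit can drop out of the efficacy counts

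*Combined protocol and SAP*

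**What the plan says.** Section 10 sets the visits: "Clinical Assessments will be done at baseline post crown placement; at months 3, 6, 12 and 18; and end of study visit occurring" between 24 and 30 months. Retention and clinical pulp pathology are graded at each follow-up visit; radiographic pulp pathology is graded at 24 months only.

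Outside that schedule the plan has one provision: "Non-recall assessment to be done at the time of tooth/crown lost to study due to trauma". It continues: "If this was to occur, the patient would be discontinued from study and the justification recorded". There is no matching provision for a tooth or crown lost, removed or repaired for another reason.

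Appendix 12 grades clinical pulp pathology as Absent or Present. Appendix 8 grades retention as Intact, partially missing, or one of four Missing codes that differ by where cement remains. One code reads "Missing – no cement remaining on tooth or crown"; another reads "Missing – some or all cement remaining on crown interior (if crown available"). None covers a crown that came off and was put back or replaced.

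Section 11.0 names crown retention and clinical pulp pathology among the primary efficacy variables, keeps subjects with lost crowns or teeth in the efficacy set, and adds: "Any missing, unused or false data will be omitted from data analysis".

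**The concern.** Pulp disease leading to extraction, and debonding followed by recementation, need not wait for a study visit. If they are dealt with in a gap, the next visit finds either no tooth to grade or a crown that looks sound. Failures treated early could then be lost from the efficacy data while those persisting to a visit are kept. The loss would be selective, and it would fall on two primary efficacy variables. Section 4 describes the trial as non-blinded, so leaving examiners to decide case by case how to grade such teeth also opens the way to different handling by arm.

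**Working it through.** The plan states no event rate and no power calculation, so there is no figure of its own to reproduce. The check is a reading of the text followed by an illustration.

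**Gaps between visits** (Section 10). Visits at 0, 3, 6, 12, 18 and 24 to 30 months give gaps of 3, 3, 6, 6 and 6 to 12 months (24 − 18 = 6; 30 − 18 = 12).

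**A tooth sound at month 12 and extracted for an abscess at month 15.**
- Section 10: not a trauma loss, so no unscheduled assessment is called for.
- Month 18, Appendix 12: there is no tooth to examine, no code for an extracted tooth, and no rule that the extraction counts as Present.
- Section 10 also lists an assessment of the tooth at every interval, but no appendix gives it a scale.
- Month 24 radiograph: the tooth is gone, so it cannot recover the event.
- Section 11.0: an empty score is missing, and missing data are omitted.

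**A crown that comes off between visits.**
- Still off at the next visit: graded Missing (C1 to C4). What is lost is the date and perhaps the cement detail, since C3 and C4 depend on having the crown.
- Recemented or replaced before the next visit: no grade applies, and Intact is the grade that fits what the examiner sees.

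**Illustration for pulp pathology.** Let r be the true share of teeth affected and e the share of those extracted unscored and omitted. Both are assumptions. The omitted teeth leave numerator and denominator, so

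scored rate = r(1 − e) / (1 − re).

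| r | e = 0 | e = 25% | e = 50% |
|---|---|---|---|
| 5% | 5% | 0.0375/0.9875 = 3.8% | 0.025/0.975 = 2.6% |
| 10% | 10% | 0.075/0.975 = 7.7% | 0.05/0.95 = 5.3% |
| 15% | 15% | 0.1125/0.9625 = 11.7% | 0.075/0.925 = 8.1% |

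**In teeth.** Section 6 expects about 120 to 200 crowns, or 40 to 67 per arm if split equally. At r = 10% and e = 50%, the events lost are 120 × 0.10 × 0.50 = 6 to 200 × 0.10 × 0.50 = 10 overall, about 2 to 3 per arm, out of 4.0 to 6.7 expected per arm.

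**Illustration for retention.** A recemented crown graded Intact stays in the denominator, so the scored failure rate is r(1 − e). With the same assumed 10%, this is 0.10 × 0.75 = 7.5% or 0.10 × 0.50 = 5.0%.

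These are cumulative rates. Section 11.0 compares arms visit by visit, so the effect at any one visit would differ.

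**The case against.** The strongest reply is that the events are not invisible.

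- **Adverse events.** Section 9 defines these broadly, related or not, and records onset and remedy independently of the visit schedule. Section 11.0 tabulates them for everyone with a crown placed. An abscess with extraction fits. This stands for safety: a reader might infer that the harm disappears from the trial, and the documents do not support that. But nothing carries the adverse event record into the tooth-level pulp variable compared between arms.
- **Efficacy set.** Subjects with lost teeth stay in, whatever the cause. True, but membership of the set does not supply a score.
- **Earlier detection.** Pulp disease visible at a scheduled visit is graded Present at that visit. This also stands; only disease that arises and is treated within a gap is at risk.
- **Sensible grading.** Nothing forbids an examiner from entering Present for a tooth known to have been extracted for pulp disease. Equally, nothing requires it. So the score may be missing; it is not certain to be.
- **Debonding.** A reader might infer that any crown debonded between visits goes unscored. Appendix 8 contradicts this: a crown that remains off is graded Missing at the next visit. Only recemented or replaced crowns are exposed.

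A reader might also infer that arms with acute failures will look better than arms with slow ones. If the unscored share were 25% in one arm and 75% in another, equal true rates of 10% would appear as 7.7% and 2.7%. At 40 crowns per arm, however, that is 3/39 against 1/37, a difference of two teeth in a pilot, and no passage suggests that the shares differ by arm.

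**Conclusion.** The concern holds in a limited form. The plan has no rule for grading pulp outcome when a tooth is extracted for a non-trauma reason between visits, and no retention grade for a crown recemented or replaced before the next visit. With missing data omitted, both primary variables can be undercounted in the efficacy analysis.

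The size is unknown. It depends on the true event rate and on the share of events resolved between visits, neither of which the documents give. The illustrated fall from 10% to 7.7% or 5.3% rests wholly on assumed values, and the bias is zero if every event is graded. The documents do not show that an undercount will occur, or that it would favour any arm. It is a gap in data capture that is cheap to close beforehand and hard to reconstruct afterwards.

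**What to change.** - **Section 10.** Reword the sentence so that the non-recall assessment form is completed for any loss, extraction, recementation, repair or replacement of a study tooth or crown, whatever the cause. Record the date, the cause and the Appendix 8, 9, 10 and 12 grades. If the event was treated elsewhere, take the details from the dental record, the adverse event form or the parent at the next visit.
- **Appendix 8.** Add a grade for a crown lost since the last visit and since recemented or replaced.
- **Section 11.0.** State that an extraction for pulp disease counts as clinical pulp pathology Present, that recemented or replaced crowns count as retention failures, and at which visit each event enters the comparison.
- **Section 7.5.4.** Its rule excluding teeth that need extraction sits under failure to fit and reads as applying at placement. Say whether it also covers follow-up.

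This changes what is recorded and counted, not how any child is treated. The cost is wording, a small case report form change and some extra form completion. Entry is restricted to the Center's own patients (Section 6.1), so many events should be traceable, but cause will be less certain for those treated elsewhere.

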6. STUDY POPULATION

Ninety (90) subjects contributing to approximately 120 to 200 crowns on primary teeth will be recruited from the patient pool of the Center for Pediatric Dentistry who receive care under general anesthesia and enrolled into the study. A maximum of four crowns will be placed in any subject. It is estimated that it will take approximately 24 weeks to place all crowns and complete the baseline examination.

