7.4 Treatment Randomization

Restorations will be randomly allocated to a patient; all teeth in a single patient will be randomly allocated to receive one of the restoration treatments: 1) NuSmile Signature crowns (thirty patients in the intervention group 2) NuSmile ZR crowns (thirty patients in the intervention group and 3) and composite strip crowns (thirty patients in control group).

The randomization sequence will be created using STATA 12.0 (StataCorp, College Station, TX) statistical software using random block sizes, which are known only to the study statistician. The randomization list will be created and placed in the order determined above into opaque sealed envelopes prior to trial start. The envelopes will be kept in a secure place known only to the study coordinator, research assistants, and statistician.

Each patient will be assigned a random treatment when they arrive at the treatment appointment and after they have been determined eligible and have signed the consent form. The clinician will be told the treatment assignment immediately prior to the treatment appointment.

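### Losing one study tooth or crown to trauma removes the whole child, so scheduled outcome follow-up of the child's other study crowns stops

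*Combined protocol and SAP*

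**What the plan says.** Section 10 (Study Assessments) ends with a rule for a tooth or crown lost to trauma. A non-recall assessment is done at the time of the loss, and then: "If this was to occur, the patient would be discontinued from study and the justification recorded". It makes no exception for a child who still has other study crowns.

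The related provisions are:

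- Section 6 expects "Ninety (90) subjects contributing to approximately 120 to 200 crowns on primary teeth" and adds: "A maximum of four crowns will be placed in any subject".
- Section 7.4 randomizes by child: "all teeth in a single patient will be randomly allocated to receive one of the restoration treatments".
- Section 11.0 lists among the primary efficacy variables "crown retention, veneer/composite integrity, secondary caries, occlusal integrity, history of trauma". It plans logistic models fitted by GEE to allow for clustering, without defining the cluster.
- Section 11.0 also states that "subjects who have lost crowns or teeth will be considered for efficacy", and that "Any missing, unused or false data will be omitted from data analysis".
- Section 12.2 gives three reasons for withdrawing a subject; traumatic loss of a tooth or crown is not one of them. It leaves to the Principal Investigator whether a withdrawn subject needs more treatment or observation.
- Appendix 8 has retention codes for a missing crown (C1 to C4), whatever the cause.

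**The concern.** The event is defined for a tooth or crown and the consequence for a patient. A child with four study crowns who loses one to a fall leaves the study with three crowns that could still be assessed. No section keeps those crowns on the scheduled visits; the Principal Investigator's discretion in section 12.2 is not scheduled outcome assessment. Their later scores are then missing, and section 11.0 omits missing data.

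Two things make this more than an untidy sentence. First, the exit is linked to outcomes: it is triggered by an event that bears on crown retention and history of trauma. An ordinary GEE analysis of the available data relies on data missing completely at random, and an exit triggered by an outcome event puts that in doubt. Second, the chance of exit rises with the number of crowns, so the children who contribute most crowns leave most often. At stake is usable follow-up in arms of only 30 children.

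**Working it through.** **Inputs from the documents.** 90 children, 30 per arm (section 5); about 120 to 200 crowns, at most four per child (section 6); one treatment per child (section 7.4).

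**Inputs that are assumed.** The documents give neither a trauma rate nor the spread of crowns per child. I take the chance p that a crown is lost to trauma during the study as 5% (range 2–10%), and the within-child correlation of losses ρ as 0, 0.3 or 0.5. I take the lowest and highest results over every mix of 1 to 4 crowns in 90 children.

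**The plan's own figures.** 3 × 30 = 90. Crowns per child: 120/90 = 1.33 to 200/90 = 2.22. With 120 crowns there are 30 beyond one per child, so between 30/3 = 10 and 30 children have more than one. With 200 crowns there are 110 beyond one per child, so between 37 (110/3 = 36.7, rounded up) and 90 children do.

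**Step 1: per child.** For a child with m crowns, let P0(m) be the chance that none is lost to trauma. The expected number of remaining crowns whose follow-up ends is

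m × [(1 − p) − P0(m)].

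With independent losses, P0(m) = (1 − p)^m. With clustered losses I use a beta-binomial: P0(m) is the product over i = 0 to m − 1 of (b + i)/(a + b + i), with a + b = 1/ρ − 1 and b = (1 − p)(a + b). At p = 5%:

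| Crowns m | ρ = 0 | ρ = 0.3 | ρ = 0.5 |
|---|---|---|---|
| 1 | 0 | 0 | 0 |
| 2 | 2(0.95 − 0.9025) = 0.095 | 2(0.95 − 0.91675) = 0.0665 | 2(0.95 − 0.92625) = 0.0475 |
| 3 | 3(0.95 − 0.8574) = 0.278 | 3(0.95 − 0.8921) = 0.174 | 3(0.95 − 0.9108) = 0.118 |
| 4 | 4(0.95 − 0.8145) = 0.542 | 4(0.95 − 0.8726) = 0.310 | 4(0.95 − 0.8994) = 0.202 |

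Under independence the child's chance of exit, 1 − P0(m), is 5.0%, 9.8%, 14.3% and 18.5% for 1 to 4 crowns.

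**Step 2: whole trial at p = 5%.** The lowest totals come from spreading crowns evenly: 60 children with one and 30 with two (120 crowns), or 70 with two and 20 with three (200 crowns). The highest come from concentrating them: 80 with one and 10 with four (120), or 53 with one, 1 with three and 36 with four (200).

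| | 120 crowns | 200 crowns |
|---|---|---|
| ρ = 0.5 | 30 × 0.0475 = 1.4 to 10 × 0.202 = 2.0 | 70 × 0.0475 + 20 × 0.118 = 5.7 to 36 × 0.202 + 0.118 = 7.4 |
| ρ = 0.3 | 30 × 0.0665 = 2.0 to 10 × 0.310 = 3.1 | 70 × 0.0665 + 20 × 0.174 = 8.1 to 36 × 0.310 + 0.174 = 11.3 |
| ρ = 0 | 30 × 0.095 = 2.9 to 10 × 0.542 = 5.4 | 70 × 0.095 + 20 × 0.278 = 12.2 to 36 × 0.542 + 0.278 = 19.8 |

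**Step 3: other loss rates, independent losses.** At p = 2%: 1.2–2.3 of 120, or 5.1–8.4 of 200. At p = 10%: 5.4–9.8 of 120, or 22.9–35.6 of 200. The top figure needs the highest rate, full independence and the most concentrated mix together.

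**Step 4: timing.** These are counts of crowns, not of visits. If losses were spread evenly over 24 months (assumed), an exit would remove on average (6 + 12 + 18 + 24)/(4 × 24) = 62.5% of a remaining crown's four analysed follow-up visits, and always the 24-month one.

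**Under a tooth-level rule** the number of remaining crowns leaving follow-up for this reason is 0.

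**The case against.** The strongest reply is that little is lost and nothing is hidden. The loss is documented at the non-recall assessment, Appendix 8 can code it, section 11.0 keeps the child in the efficacy set, and data collected before the exit remain. All of that stands, and it rules out one tempting inference: that traumatic losses drop out of the retention comparison and distort it. No section says they are removed, and changing the exit rule would not alter how the lost crown is scored.

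A reader might also infer that the rule biases the comparison of arms. The documents do not show this. Children with more crowns leave more often, but allocation is random by child, so that alone creates no expected imbalance. The trial is non-blinded, but no route from that to this exit is described. Nor is section 12.2 in contradiction with section 10: its list omits this reason, which is a gap.

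Two further points limit the claim. All study crowns are on anterior teeth and one injury may involve several, so the clustered counts deserve at least as much weight as the independent ones. And a crown next to a new gap is not scoreable in every respect as before: proximal contact (Appendix 3) may be read as open because the neighbour is gone, and parents' satisfaction (Appendix 14) concerns the child's teeth overall.

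Finally, this is a convenience-sample pilot, and at 120 crowns at least 60 of the 90 children have one crown and lose no other. That lowers the importance. It does not supply a reason to stop following crowns that are still in place, in a plan that makes inferential comparisons out to 24 months.

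**Conclusion.** The point holds as a modest, inexpensive improvement. On the plain reading of section 10, one traumatic loss ends scheduled outcome assessment of up to three other study crowns, and no other section restores it. Only children with two or more study crowns are affected, and only losses due to trauma count.

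At an assumed 5% loss per crown the expected number of remaining crowns leaving follow-up is about 1–3 of 120 or 6–11 of 200 with within-child correlation 0.3–0.5, and about 3–5 of 120 or 12–20 of 200 with independent losses. These figures rest on assumed rates and are illustrative. The exit is linked to the outcomes, but bias between arms would depend on traumatic loss differing by arm, and neither its size nor its direction can be known from the documents. The firm conclusion is avoidable loss of data, not a demonstrated bias.

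**What to change.** In section 10, state that after a traumatic loss outcome follow-up ends for the lost tooth or crown only; that the child's other study crowns stay on the scheduled visits and in the GEE analysis, clustered by child; and that a child leaves outcome follow-up for this reason only when no study crown remains. Add a matching line to section 12.2. In section 11.0, name the child as the cluster and make the text agree with the new rule.

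Flag proximal-contact and parents'-satisfaction scores recorded after the loss of an adjacent tooth or crown, and add a sensitivity analysis that excludes them.

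The cost is a few sentences, a flag on the case report form, one sensitivity analysis and a few more crown assessments at visits already scheduled. The change concerns outcome follow-up and analysis only; it says nothing about the child's care.
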